6.4 Duration of Study Treatment

Treatment continues for a minimum of 2 cycles (6 weeks) and then until disease progression unless one of the following occurs:

- Patient experiences unacceptable side effects exemestane
- Patient refuses further treatment or is non-compliant
- Patient requires other anti-cancer therapy
- A greater than 6 week break from exemestane therapy occurs, regardless of cause
- In the opinion of the treating investigator, continuing on study therapy is not in the best interest of the patient

Exemestane may be continued as a single agent at the discretion treating investigator in the event the ICB therapy is permanently discontinued due to

unacceptable toxicity (refer to Appendix IV for potential risks of ICB therapy) as long as none of the above criteria is not met.

An end of treatment visit occurs 4 weeks (\pm 1 week) after the last dose of exemestane or prior to the start of a new therapy, whichever is shorter, to assess for ongoing toxicity and for the patient to return their study drug supply and daily drug log.

6.5 Duration of Study Participation

Direct study participation stops with the end of treatment visit; however all patients are followed for 1 year from the start of study treatment or until death, whichever is shorter.

Patients who discontinue treatment due to disease progression are followed for survival only (medical record review, local MD or patient contact) for 1 year from study treatment start.

Patients who discontinue treatment in the absence of disease progression are followed for disease response per standard of care until disease progression or the start of a new treatment, whichever is shorter and then for survival only for 1 year from study treatment start.

By 1 year from treatment start, all patients should have a last known date alive or a death date with cause recorded in OnCore, as well as, an initial date for disease progression in association with exemestane treatment.

7 Exemestane Drug Information

Names: exemestane, AROMASIN®, 6-Methyleneandrosta-1,4-diene-3,17-dione

Category: Aromatase Inhibitors

Indications: 1) For the treatment of advanced breast cancer in postmenopausal women whose disease has progressed following tamoxifen therapy and 2) adjuvant treatment of postmenopausal women with estrogen-receptor positive early breast cancer who have received two to three years of tamoxifen and are switched to exemestane for completion of a total of five consecutive years of adjuvant hormonal therapy.

Pharmacology: Aromatase is an enzyme that converts hormones to estrogen in the body's adrenal glands. The aromatase inhibitors (AIs) are drugs that reduce estrogen levels by blocking the action of aromatase in the adrenal glands. The selective AIs (SAIs) selectively reduce levels of estrogen without interfering with levels of other

steroid hormones that are produced by the adrenal gland. Drugs in this class include anastrozole (Arimidex™), letrozole (Femara™) and exemestane (Aromasin™)

Availability: For the purposes of this study a commercial formulation of Aromasin will be provided by the manufacturer, Pfizer. The study specific drug reorder form is attached in OnCore under this study. It is recommended that a drug inventory sufficient to treat study subjects for approximately four (4) weeks be maintained while waiting for additional ordered supplies.

Drug Accountability: The study drug supply will be stored and dispensed by the University of Minnesota Medical Center, Fairview Investigational Drug Services (IDS) Pharmacy. IDS will be responsible for drug accountability through the study. IDS will provide study drug to participating MNCCTN sites.

Dosage and Administration Schedule: One 25 mg tablet once daily after a meal

Dose Forms and Strengths: Aromasin Tablets are round, biconvex, and off-white to slightly gray. Each tablet contains 25 mg of exemestane. The tablets are printed on one side with the number "7663" in black.

Storage and Stability: Store at 25°C (77°F); excursions permitted to 15°–30°C (59°–86°F).

Drug Return/Destruction: At the end of the study and after final reconciliation, IDS will destroy any remaining drug according to their current SOP.

Expected Side Effects: refer to Section 6.1.1.

FDA Pregnancy Category X

Contraindications and Counseling:

Patients with a known hypersensitivity to the drug or to any of the excipients

Women of premenopausal endocrine status, including pregnant women

Patients should be informed that they should not take estrogen-containing agents while they are taking exemestane as these could interfere with its pharmacologic action.

Patients should be informed that AROMASIN lowers the level of estrogen in the body. This may lead to reduction in bone mineral density (BMD) over time. The lower the BMD, the greater the risk of osteoporosis and fracture.

Refer to the Aromasin Prescribing Information ([https://www\(pfizer.com/products/product-detail/aromasin](https://www(pfizer.com/products/product-detail/aromasin)) for additional information

8 Measurement of Effect

For the purposes of this study's primary endpoint, patients should be re-evaluated for response every 6 weeks.

Response and progression will be evaluated in this study using the revised Response Evaluation Criteria in Solid Tumors (RECIST) guideline (version 1.1) [*Eur J Ca* 45:228-247, 2009]. Refer to Appendix II for the complete RECIST guidelines.

Quality of life scores, as measured by PROMIS, will be evaluated descriptively at baseline, every 3 weeks during and at the end of treatment visit using medians, ranges, interquartile ranges and boxplots to look for trends in various areas measured by PROMIS.

9 Schedule of Activities

Note: Study visits are scheduled every 3 weeks independent of the immune checkpoint blockade therapy administration per standard of care. During exemestane a ± 2 day window is permitted for every 3 week visits (start of new treatment cycle) and a ± 7 day window is permitted for the every 6 week disease reassessment. The end of treatment (EOT) visit 30 days after the last dose of study drug may be performed with a ± 7 day window. Follow-up visits are per standard of care with disease status and survival status abstracted from the medical record.

9.1 Schedule of Patient Tests and Procedures

	Baseline (within 14 days of enrollment)	During Exemestane Therapy		End of Treatment Visit 4 weeks \pm 1 week) after final dose of exemestane	Follow-up	
		Every 3 weeks (\pm 2 days)	Every 6 weeks (\pm 1 week)		disease response (until PD or start of new therapy)	survival at 1 year (all patients)
ASSESSMENTS						
Witten consent	X					
Medical history	X	X		X		
Review of prior anti-cancer therapy	X					
Concomitant meds	X	X				
Physical exam	X	X				
Vital Signs	X	X				
Weight	X	X				
ECOG Performance status	X	X				
Disease re-assessment			X		X	
Symptom and toxicity notation (pt diary)	X	X		X		
LABORATORY EVALUATIONS						
CBC/diff, plts	X	X				
Comprehensive Metabolic Profile (CMP)	X	X				
Estradiol assay ²	X					
SCANS AND PROCEDURES						
CT of chest/abd/pelvis	X ¹		X	X (if not done in previous 6 weeks)	X ⁴	
MRI or CT of brain if previous hx of CNS dz or as clinically indicated	X ¹					
DEXA scan	X ¹ (perform only if none in previous 12 months)	repeat every 12 months				
CONTINUATION OF STANDARD OF CARE IMMUNE CHECKPOINT INHIBITOR THERAPY						
Nivolumab pembrolizumab, or atezolizumab	Continue per SOC while maintaining every 3 week visits for exemestane					
RESEARCH RELATED						
Exemestane		25 mg po once a day every day				
Research staff "check-in" ³		Cycle 1 only between Day 8 and 12				
Reconciling of Exemestane tablets		X		X		
Quality of Life Questionnaire (PROMIS-29 Profile)	X	X		X		
Monitoring for stopping rule events		Refer to Section 10.3				
Blood Samples 30 ml serum (red top) 20 ml EDTA (purple top) 20 ml cell-free DNA BCT tube	X	X prior to cycle 2, 3, and 5		X		
Blood Samples 10 mL green top tube for PBMC	X	X prior to Cycle 2 and 3				
biopsy material ⁵	X	at the time of biopsy for clinical reasons				

1 Within 4 weeks of study enrollment

2 For women < 55 years of age

- 3 A member of the research staff will contact the patient to see how things are going (screen for toxicity) and if they have any questions
- 4 Per standard of care for patients who discontinued exemestane for reasons other than disease progression – abstract results from medical record
- 5 At enrollment archived from original diagnosis will request 15 unstained slides but require a minimum of 5 unstained slides for eligibility or resection and fresh at any time tissue is obtained for clinical reasons (i.e. SOC) - consent for tissue is embedded in the treatment consent

All research blood samples go to the Masonic Cancer Center's Translational Therapy Lab (TTL).

Research sample collection and questionnaire completion is tied to the clinical care schedule of events and their associated window for performance. Therefore, if a clinical time point does not occur or is altered, the research related time point will be adjusted (or eliminated) as appropriate.

9.2 Research Related Tests and Procedures

The PROMIS-29 Profile (Appendix VI) will be completed before starting exemestane, every 3 weeks while taking the study drug, and at the end of treatment visit.

Correlative studies will examine biomarkers in the Estrogen Receptor (ER) pathway including circulating levels of hormones and products of ER response genes. DNA will be extracted from blood collected at baseline, during treatment, and at progression and sent for sequencing using the Guardant360 assay to determine if mutations are present that are correlated with resistance to an aromatase inhibitor. Three hundred sixty (360) common mutations will be analyzed that have been used to monitor breast cancer patients on aromatase inhibitor therapy. Additionally, since cigarette smoking is associated with increased ER expression²⁹, we will measure serum cotinine in patients at baseline as a measure of recent tobacco smoke exposure.

Tumor tissue will be analyzed ER β receptor expression and aromatase at baseline using immunohistochemistry (IHC). Additionally, we will analyze PDL-1 expression if not already done for clinical reasons. Finally, we will evaluate tumor sections for CD8 T cell staining and MDSC on archival tissue as well as any post-treatment tissue obtained.

Finally, peripheral blood mononuclear cells (PBMCs) will be obtained at baseline and prior to Cycle 2 and 3 to evaluate the peripheral immunophenotype prior to and after initiation of exemestane.

10 Adverse Event Monitoring, Recording and Reporting

Toxicity and adverse events will be classified according to NCI's Common Terminology Criteria for Adverse Events V 4.0 (CTCAE).

A copy of the CTCAE can be downloaded from the CTEP home page <http://evs.nci.nih.gov/ftp1/CTCAE/About.html>

10.1 Definitions

Note: throughout this section the generic term "drug" refers to the exemestane.

The following definitions are based on the Code of Federal Regulations Title 21 Part 312.32 (21CFR312.32(a)).

Adverse Event: Any untoward medical occurrence associated with the use of a drug in humans, whether or not considered drug related.

Suspected Adverse Reaction: Any adverse event for which there is a reasonable possibility that the drug caused the adverse event.

Life-Threatening Adverse Event Or Life-Threatening Suspected Adverse Reaction: An adverse event or suspected adverse reaction is considered "life-threatening" if, in the view of either the investigator or sponsor, its occurrence places the patient or subject at immediate risk of death.

Serious Adverse Event Or Serious Suspected Adverse Reaction: An adverse event or suspected adverse reaction is considered "serious" if, in the view of either the investigator or sponsor, it results in any of the following outcomes:

- Death
- A life-threatening adverse event
- Inpatient hospitalization or prolongation of existing hospitalization
- A persistent or significant incapacity or substantial disruption of the ability to conduct normal life functions
- A congenital anomaly/birth defect.

Important medical events that may not result in death, be life-threatening, or require hospitalization may be considered serious when, based upon appropriate medical judgment, they may jeopardize the patient or subject and may require medical or surgical intervention to prevent one of the outcomes listed in this definition.

Unexpected Event: An adverse event or suspected adverse reaction is considered "unexpected" if it is not listed in protocol-related documents (e.g. protocol, consent documents, investigator brochure, package insert), or is not

listed at the specificity or severity that has been observed or given the characteristics of the subject population being studied.

Attribution: is the relationship between an adverse event or serious adverse event and the study drug. Attribution is assigned as follows:

- Definite – The AE is clearly related to the study drug
- Probable – the AE is likely related to the study drug
- Possible – the AE may be related to the study drug
- Unlikely – the AE is doubtfully related to the study drug
- Unrelated – the AE is clearly not related to the study drug

Attribution must be assigned by the treating physician or the PI.

The following definitions are from the Masonic Cancer Center's Data and Safety Monitoring Plan (<http://z.umn.edu/dmsp>)

Major Deviation: A deviation or violation that impacts the risks and benefits of the research; may impact subject safety, affect the integrity of research data and/or affect a subject's willingness to participate in the research. Deviations that place a subject at risk, but do not result in harm are considered to be major deviations.

Minor Deviation: A deviation or violation that does not impact subject safety, compromise the integrity of research data and/or affect a subject's willingness to participate in the research.

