10.2.2 Event Documentation

Adverse events occurring after the initiation of exemestane treatment through and including 28 calendar days after the last dose must be documented. Refer to Section 6.1.1 for a list of expected toxicities of exemestane and Appendix IV for a list of expected toxicities for the ICB therapy.

Since a key outcome parameter of this study is to characterize the toxicities of exemestane in combination with an FDA approved immune checkpoint inhibitor in this patient population, adverse event documentation requirements will be

determined based on grade, expectedness and relationship to study therapy as follows:

	CTCAE Grade 1	CTCAE Grade 2		CTCAE Grade 3		CTCAE Grade 4 and 5
	Expected or Unexpected	Expected	Unexpected	Expected	Unexpected	Expected or Unexpected
Unrelated Unlikely	Not required	Not required	Not required	Not required	Required	Required
Possible Probable Definite	Not required	Not required	Required	Required	Required	Required

In addition any event meeting the definition of a serious adverse event (SAE) regardless of attribution that occurs during this period will be documented in the source document and recorded in OnCore.

After the end of treatment visit, monitoring for adverse event will become less frequent based on the schedule in Section 9 and only events at least possibly related to study treatment (based on the table above) will be documented upon knowledge.

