10.3 Stopping Rule Events

For the purpose of this protocol any Grade 4 or 5 treatment related event and any Grade 3, 4, or 5 immune related adverse event (pneumonitis, colitis, nephritis, myocarditis or hepatitis) will be considered excess toxicity per Section 13.4 and be reported as a stopping rule event using the Event Form found in OnCore.

Events that count toward an early study stopping rule do not necessarily constitute an event requiring expedited reporting and should only be reported as such if they meet the criteria found in Section 10.5.

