10.4 SAE and Death Documentation

The reporting period for this study is from initiation of study treatment (exemestane) through and including 28 days after the last dose of exemestane. However, after this time point, the investigator must report upon knowledge any study treatment related meeting the definition of a serious adverse event (SAE) using the MCC SAE Report Form in OnCore.

Deaths, including due to disease, within the follow-up period will be recorded as an SAE. Deaths due to disease should be recorded as a Grade 5 “Neoplasms benign, malignant and unspecified (including cysts and polyps) – Other (Progressive Disease).

In addition, upon knowledge, the death date and cause must be reported in the patient follow-up tab in OnCore using the comment field in the survival status section to record the cause.

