12.2 Secondary Endpoints

Toxicity will be assessed from the 1st dose of exemestane through 30 days after the last dose, or the start of a new anti-cancer treatment, whichever is earlier. Toxicity severity will be graded using the Common Toxicity Criteria for Adverse Events (CTCAE) version 4. Attribution and expectedness will be assigned per the definitions found in Section 10.1.

Response duration, progression-free survival and survival will be assessed until 1 year after study enrollment based on the definitions found in RECIST 1.1 (Appendix II).

Quality of life will be assessed by use of PROMIS-29 at baseline, every 3 weeks while on study drug and at the end of treatment visit.

13 Statistical Considerations

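### Attribution is defined against exemestane alone, so Grade 3 toxicity of the combination can go unrecorded and the events that feed the 13.4.1 stopping rule are not fixed

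*Combined protocol and SAP*

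**What the plan says.** The aim is the combination. Section 1.2 asks for the toxicity profile of exemestane with checkpoint blockade, and 10.2.2 gives as a key outcome to "characterize the toxicities of exemestane in combination with an FDA approved immune checkpoint inhibitor in this patient population".

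The tools refer to one agent. In Section 10.1 the generic term for drug "refers to the exemestane", and attribution "is the relationship between an adverse event or serious adverse event and the study drug". Section 10.4 sets the reporting period as running "from initiation of study treatment (exemestane) through and including 28 days after the last dose of exemestane", which equates study treatment with exemestane. Section 12.2 ties the toxicity endpoint to this scale: "Attribution and expectedness will be assigned per the definitions found in Section 10.1". Section 13.1 takes the toxicity endpoint as described in 10.2.2.

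The 10.2.2 table decides what is documented by grade, expectedness and relationship to *study therapy*, a term it does not define. In the Unrelated/Unlikely row, an expected Grade 3 event is not required. The same section names Appendix IV as the list of expected checkpoint-inhibitor toxicities.

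Section 10.3 counts "any Grade 4 or 5 treatment related event and any Grade 3, 4, or 5 immune related adverse event" as stopping-rule events. The immune-related part is limited to pneumonitis, colitis, nephritis, myocarditis and hepatitis. Section 13.4.1 monitors the Grade 4/5 treatment-related events and 13.4.2 the five named toxicities.

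**The concern.** The rationale in Section 2.2 is that lowering estradiol should reverse immunosuppression and so help the checkpoint inhibitor. More immune toxicity is therefore a foreseeable harm. It would look like ordinary checkpoint-inhibitor toxicity, and 6.1.1 tells investigators to expect no change in the toxicity profile. With a single arm, an event due to the checkpoint inhibitor alone cannot be told apart from one that exemestane made worse.

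A site with only an exemestane scale could reasonably rate such an event Unlikely. Two things are then at stake. The reported toxicity profile may omit Grade 3 events that belong to the combination. And two sites could classify the same Grade 4 event differently for 13.4.1, so the operating characteristics printed there would not describe the rule as applied.

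**Working it through.** **Which events are lost.** The table and the stopping-rule text, set side by side, for an event rated Unrelated or Unlikely to exemestane, up to 28 days after the last dose:

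| Event | Documented under 10.2.2? | Counts toward a stopping rule? |
|---|---|---|
| Grade 3, expected, non-serious, not one of the five | No | No (neither rule covers it) |
| Grade 3, expected, non-serious, one of the five | No by the table; must be reported under 10.3 | Yes, 13.4.2 |
| Grade 4/5, one of the five | Yes | Yes, 13.4.2 |
| Grade 4/5, not one of the five | Yes | Not in 13.4.2; not in 13.4.1 if *treatment related* means exemestane |

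The first row is the recording gap, the second is a conflict within the protocol, and the fourth is the monitoring gap. Events in the fourth row could include Grade 4 diabetic ketoacidosis, adrenal insufficiency, Stevens-Johnson syndrome, encephalitis or Guillain-Barré syndrome, all listed as serious risks in Appendix IV. One caveat applies to the first two rows. Section 10.1 also treats an event as unexpected if its severity is not listed, and Appendix IV gives a grade for only a few entries (for example Grade 3 or 4 anemia), so some Grade 3 events might be argued to be unexpected.

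**Reproducing the plan's figures.** Inputs are the printed boundaries with N = 29. For 13.4.1 the halt limit is 2 events up to patient 7, 3 up to 16, 4 up to 28, then 5. For 13.4.2 it is 2 up to patient 8, 3 up to 19, then 4. With event probability p, the state is updated patient by patient:

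P_n(k) = (1 − p)·P_{n−1}(k) + p·P_{n−1}(k − 1),

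and probability reaching the limit is removed and summed as P(halt). Expected N = Σ n·P(halt at n) + 29·P(no halt).

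- 13.4.1: P(halt) = 9.1% at p = 5% (stated limit 10%). At p = 20%, P(halt) = 86.7% and expected N = 13.55 (stated 87% and 13.5). Reproduced.
- 13.4.2: P(halt) = 7.0% at p = 4% (stated limit 10%). At p = 20%, P(halt) = 89.3% and expected N = 12.7 (stated 90% and 11.5). The halting probability is close; the expected N is not matched exactly. That does not affect this point.

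**Effect on halting.** The documents do not say what share of events would be attributed to the checkpoint inhibitor alone, so it is varied. Let f be that share of a true 20% Grade 4/5 rate, and g the part of those events that falls among the five toxicities. Then

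p_A = 0.20 × (1 − f) feeds 13.4.1, and p_B = 0.20 × f × g feeds 13.4.2.

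The recursion is run on both counts together, each patient having at most one event:

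P_n(a, b) = (1 − p_A − p_B)·P_{n−1}(a, b) + p_A·P_{n−1}(a − 1, b) + p_B·P_{n−1}(a, b − 1),

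halting when either limit is reached.

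| f | p_A | g = 0 | g = 0.5 | g = 1 |
|---|---|---|---|---|
| 0 | 20% | 87% | 87% | 87% |
| 0.25 | 15% | 68% | 69% | 72% |
| 0.5 | 10% | 38% | 45% | 66% |
| 0.75 | 5% | 9% | 33% | 75% |

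The table leaves out Grade 3 events among the five toxicities, and exemestane-attributed events among the five that would count in both rules. Including either would raise the halting probabilities.

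**Effect of widening the rule.** If checkpoint-inhibitor-only events entered 13.4.1 with the boundary unchanged, background events would raise the counted rate. The printed boundary halts 9.1% of the time at 5%, 25% at 8% and 38% at 10%.

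**The case against.** The strongest reply is that the protocol already catches most of what matters. Much of that stands.

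- A reader might infer that events due to the combination escape 13.4.1. They do not. Possible means "the AE may be related to the study drug", and a suspected interaction meets that. The plan's own immune rationale makes Possible a natural rating, so frequent Unlikely ratings are a risk and not a certainty.
- A reader might infer that expected Grade 3 immune events go unrecorded as a class. They do not. The five named toxicities must be reported under 10.3 with no attribution to exemestane required. Every SAE is recorded regardless of attribution, and at least possibly related Grade 3 events are required.
- A reader might infer that the plan excludes checkpoint-inhibitor events from 13.4.1 outright. It does not say so. The words are *treatment related* and *study therapy*, not *study drug*, and neither is defined. The gloss in 10.4 favors the narrow reading without settling it.
- A reader might also infer that related events would be missed in reporting to Pfizer because Appendix IV makes them expected. Section 10.6 abstracts those criteria from a manual that is not part of the documents, and 10.2.2 keeps the exemestane list (6.1.1) apart from the checkpoint-inhibitor list. That cannot be established.

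The large falls in halting need many Grade 4/5 events outside the five toxicities. Where Appendix IV gives rates for the examples above, they are low: encephalitis 0.2%, Guillain-Barré syndrome under 1%, adrenal insufficiency 0.4% to 5%. Grade 4/5 events are documented, and the data and safety monitoring council reviews the study twice a year.

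What remains is that documentation does not trigger a halt, the only relatedness scale is for exemestane, and the Grade 3 gap and the conflict with 10.3 are not answered.

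**Conclusion.** The point holds as a mismatch between a combination safety aim and a single-agent attribution scale, and should be fixed. The loss of non-serious, expected Grade 3 events rated Unrelated/Unlikely follows from the table as written if *study therapy* is read through 10.1, subject to the severity clause on expectedness. Its size cannot be estimated from the documents. The 10.2.2 and 10.3 instructions for the five named Grade 3 toxicities conflict on that same reading and must be reconciled.

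For 13.4.1 the defect is an undefined event, not a faulty boundary: the printed figures reproduce. With f = 0.5, halting at a true 20% rate is between 38% and 66% instead of 87%. These results rest on assumed attribution shares and at most one event per patient, and they illustrate the sensitivity without predicting what will happen. The documents do not support calling the safety monitoring blind to immune toxicity.

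**What to change.** 1. In 10.1, record attribution separately to exemestane and to the checkpoint inhibitor for each event.
2. In 10.2.2, define *study therapy* as either agent or both for the Possible/Probable/Definite row, and state that every 10.3 event is documented whatever its table cell.
3. In 10.3 and 13.4.1, state which agents *treatment related* covers. If it means exemestane only, say so, and acknowledge that Grade 4/5 events due to the checkpoint inhibitor alone and outside the five toxicities have no stopping boundary. If it includes them, re-justify the 5% reference rate and recompute the boundary. That choice is more than a wording change.

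The cost is one more adverse-event field, more Grade 3 recording, and possibly a revised boundary. A wider definition would make a halt more likely, but under 13.4 a halt leads to review by the study committee and not to automatic closure.
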